3.1. Changes from study protocol

All analyses detailed in this document are as specified in the protocol and subsequent amendments, no major changes from the protocol-planned primary analysis have been performed. The only exception is the PK data analysis, for which no estimation of individual PK parameters will be conducted by using a population PK approach. Plasma concentrations of MEN1611 by time-point will be summarised by descriptive statistics only.

4. Study overview

MEN1611 is a potent and selective Class I PI3K inhibitor with a novel structure. In particular, it has potent inhibitory activities against Class I PI3K α . MEN1611 is yellow to greenish yellow powder or powder with lumps, stable in the solid state. The MEN1611 drug product is a hard capsule for oral administration.

This study is designed as an Open-label, Multicenter, Phase Ib/II Study of MEN1611 and Cetuximab, to be conducted in approximately 29 sites in Europe and US.

Phosphatidylinositol 3-kinase, catalytic, alpha polypeptide gene (PIK3CA) mutated, N-K-RAS and BRAF wild type, metastatic colorectal cancer, in patients failing irinotecan, oxaliplatin, 5-FU and anti- epidermal growth factor receptor (EGFR) containing regimens will be enrolled.

The study is aimed to determine the RP2D of MEN1611 when administered orally in combination with cetuximab during the first step of the study, and to assess the anti-tumor activity of MEN1611 in combination with cetuximab during the second step.

4.1. Study objectives

1.1. Primary objective(s)

Step 1:

- To determine the RP2D of MEN1611 when administered orally in combination with cetuximab to patients with PIK3CA mCRC failing irinotecan, oxaliplatin, 5-FU, and anti-EGFR containing regimens.

Step 2:

[figure not shown]
- To assess the anti-tumour activity of MEN1611 in combination with cetuximab in patients with PIK3CA mutated mCRC failing irinotecan, oxaliplatin, 5-FU, and anti-EGFR containing regimens.

1.2. Secondary objective(s)

The following will be assessed/determined:

- To assess the safety and tolerability of MEN1611 in combination with cetuximab.
- To assess the PK profile of MEN1611 when given in combination with cetuximab

1.3. Exploratory objective(s)

5. Investigational plan

An overview of the Clinical Study Protocol will be provided in this Chapter.

[figure not shown]
5.1. Study configuration and structure

Overall Study Design and Plan Description

This is an open-label, dose-confirmation and cohort expansion, multicenter, Phase Ib/II study to be conducted in approximately 29 sites in Europe and US.

[figure not shown]
The study will consist of 2 sequential steps:

Step 1 (Confirmation of Dose for Cohort Expansion):

Step 2 (Cohort Expansion Phase):

Treatment regimen

MEN1611

Step 1 (Dose-confirmation Phase): MEN1611 as oral capsules of 16 mg strength will be orally administered BID (approximately 12 hours apart) for a continuous 28-day cycle. The starting dose of MEN1611 will be 48 mg BID for a total daily dose of 96 mg. In case 48 mg BID in combination with cetuximab will represent the toxic dose level for this combination, a lower dose level of 32 mg BID will be tested in cohort 2.

In this Phase, MEN1611 will be administered as below:

- Cohort 1: MEN1611 48 mg (3 × 16 mg) capsules BID over 28-days' cycle.
- Cohort 2: MEN1611 32 mg (2 × 16 mg) capsules BID over 28-days' cycle.

Step 2 (Cohort-expansion Phase): MEN1611 as oral capsules will be orally administered BID for a continuous 28-days' cycle at the RP2D as established in Step 1.

MEN1611 capsules should be taken with a glass of water in fasting condition, i.e. at least 2 hours after a meal and at least 1 hour before the next meal. Patient should take capsules at approximately the same time each day. At Visit 2, Visit 3 and Visit 4 of Cycle 1, and at each following visits, MEN1611 will be administered at site using the new boxes dispensed at each visit.

[figure not shown]
Cetuximab

In both Step 1 and Step 2, Cetuximab (solution for infusion) will be administered IV weekly on Day 1, 8, 15 and 22 of every 28-day cycle according to institutional standards. The initial cetuximab dose is 400 mg/m² administered as a 120-minute infusion on Day 1 of Cycle 1, followed by a weekly 250 mg/m² dose administered as a 60-minute IV infusion. Premedication with a H1 receptor antagonist (e.g. d-chlorpheniramine or diphenhydramine) and a corticosteroid is required prior to cetuximab administration (see Section 8.4.8). Management of infusion reactions due to cetuximab are to be managed according to Section 8.4.5. MEN1611 will be given in combination with weekly IV infusion of cetuximab until objective disease progression is

documented or another criterion for discontinuation is met. If cetuximab needs to be discontinued due to toxicity, continuation with MEN1611 as monotherapy should be considered and discussed with the Sponsor.

5.2. Schematic study design

You find below the schematic study design of Dose-Confirmation (Step 1) and Cohort-Expansion (Step 2).

BID = twice daily, RP2D = Recommended Phase 2 Dose.

Note: RP2D to be tested in Step 2 is the 48 mg BID or 32 mg BID if no more than 1 DLT occurs in a total of 6 patients treated in Cohort 1 or in Cohort 2, respectively in Step 1.

5.3. Study flow chart

[figure not shown]

Study code: MEN1611-02

Statistical Analysis Plan (SAP)

EudraCT/IND/NCT no.: 2019-003727-38

Version n.2.0, 11AUG2023

[figure not shown]

Study code: MEN1611-02

Statistical Analysis Plan (SAP)

EudraCT/IND/NCT no.: 2019-003727-38

Version n.2.0, 11AUG2023

[figure not shown]

Study code: MEN1611-02

Statistical Analysis Plan (SAP)

EudraCT/IND/NCT no.: 2019-003727-38

Version n.2.0, 11AUG2023

5.4. Study Endpoints

5.4.1. Primary endpoints

Step 1 (Identification of Dose for Cohort Expansion)

- Identification of the dose for the Cohort Expansion, defined as the highest dose level (maximum dose tested 48 mg BID, minimal dose tested 32 mg BID) at which no more than 1 of 6 patients experiences a DLT (see DLT definition) during the DLT assessment window (28 days) or the maximum dose judged to be tolerable by the DSC.
- The DSC will review and evaluate all the available safety data, any DLTs and PK data collected during Step 1, in order to confirm the RP2D to be tested in Step 2.

Step 2 (Cohort Expansion Phase)

- ORR defined according to RECIST v1.1 assessment locally performed using CT scan or MRI of the chest and abdomen (including pelvis and adrenal glands). Any other areas of disease involvement should be additionally investigated based on signs and symptoms of the individual patient.

5.4.2. Secondary endpoints

- *Safety and tolerability:*
 - Incidence, severity as per CTCAE v. 5.0 grading, seriousness and treatment-causality of TEAEs.
 - Frequency of clinically significant abnormalities in physical examination, safety laboratory tests, urinalysis, vital signs and 12-lead ECG.
- *PK profile:* MEN1611 plasma concentration-time data will be summarised descriptively.
- *Disease Control Rate (DCR)* defined as percentage of patients whose disease shrinks or remains stable over a certain time period. DCR is the sum of the BOR of complete, partial and stable disease rates according to local assessment.
- *Objective Response Rate (ORR)* defined as percentage of patients who had a BOR of complete response (CR), or (PR) partial response to therapy.
- *Duration of response* defined as time from first occurrence of a BOR of PR, CR or SD as locally assessed, until the disease has been shown to progress following treatment. Subjects, with a previous response, who do not show a relapse or die without recording a relapse are censored at their last available relapse-free tumor assessment date. Subjects with only one tumor assessment after baseline showing a PD, are not included in the calculation. Please refer to Attachment A for the complete Censoring Rules list.
- *Progression Free Survival:* Defined as the number of days between the first study treatment

administration to the date of first documented disease progression as per local assessment, relapse or death from any cause. Responding patients and patients who are lost to follow-up are censored at their last tumour assessment date. Please refer to Attachment A for the complete Censoring Rules list.

- *Overall Survival:* Defined as the number of days between the first study treatment administration and death from any cause. Patients still alive, that have withdrawn the study, are censored using the latest among end of study and follow-up dates. Drop-out patients are considered censored and the last available date in which the subject is known to be alive will be considered.

For the baseline assessment, CT scan or MRI should be performed no more than 4 weeks before the start of study treatment. Follow-up assessment will be performed every 2 cycles during study treatment starting from Day 1 Cycle 3 (within a window of 7 days before the visit date) until objective disease progression as defined by RECIST v1.1 or at the End of Study Visit. Any other site at which a new disease is suspected should be appropriately imaged. If an unscheduled assessment is performed and the disease has not progressed, subsequent assessments should be performed at their scheduled visits.

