12.1. Efficacy analysis

The following parameters will be summarized by cohort and overall (if appropriate) on the Efficacy population:

- Best Overall Response
- Disease Control Rate
- Objective Response Rate
- Duration of response (DoR)
- Progression Free survival (PFS);
- Overall Survival (OS).

ORR locally assessed is the primary endpoint of the Cohort Expansion Phase. All efficacy

endpoints related to tumour assessment will be evaluated considering both local (secondary endpoints) and central (exploratory endpoints) radiology assessments.

Best Overall Response (BOR) is derived as follows:

- If a subject has at least one overall response of CR, then BOR is CR;
- If a subject doesn't have any overall response of CR but has at least one overall response of PR, then BOR is PR;
- If a subject doesn't have any overall response of CR or PR but has at least one overall response of SD (or Non-CR / Non-PD) at least six weeks after the first intake of MEN1611, then BOR is SD (or Non CR / Non PD);
- If a subject doesn't have any overall response of CR, PR, SD (or Non-CR / Non-PD) after at least 6 weeks from the first intake of MEN1611, but has at least one overall response of PD, then BOR is PD;
- In all other cases, BOR is NE.

Objective Response Rate (ORR) is calculated as the sum of BOR rates of complete response (CR), partial response (PR).

Disease Control Rate (DCR) is calculated as the sum of BOR rates of complete response (CR), partial response (PR) and stable disease (SD).

Overall Survival (OS) is calculated as:

- In case of all-cause death:
OS = date of death - date of first study treatment administration + 1;
- In case of censored information not for drop-out:
OS = date of end of observation period (i.e. maximum between end of study and last follow up date) - date of first study treatment administration + 1;
- In case of censored information for drop-out:
OS = last available date in eCRF - date of first study treatment administration + 1.

Progression-free Survival (PFS) is calculated as:

- In case of death/disease progression:
PFS = date of death or date of first disease progression - date of first study treatment administration + 1
For subjects who experienced both death and progression disease, the date referred to the event that came first is considered.
- In case of censored information due to responding subjects or lost to follow-up:
PFS = date of censoring - date of first study treatment administration + 1

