Detailed censoring rules are as follows:

Circumstances		Options for end-date (progression or censoring)	Outcome
1	Documented Progression	(i) Date of documented progression	Progressed
2	Death without documented progression	(i) Date of death	Progressed
3	Documented progression or death after exactly one missing assessment	(i) Date of progression or death	Progressed
4	Documented progression or death after two or more missing assessments	(i) Date of last adequate assessment ^a	Censored
5	No documented progression and no death (with at least one post baseline assessment)	(i) Date of last adequate assessment	Censored
6	Treatment discontinuation Reason ' Disease progression/clinical progression/progression ' without radiological assessment.	(i) Ignore clinical progression and follow situations above	As per above circumstances
7	No baseline tumor assessment	Date of first study treatment administration	Censored
8	No post baseline assessment and no death	Date of first study treatment administration	Censored
9	Subject lost to follow-up (or withdrew consent) before documented progression or death	(i) Date of last adequate assessment	Censored

^aAfter the last adequate tumor assessment. Date of next scheduled assessment- as specified in the protocol

Duration of Response (DR) is calculated as:

- In case of disease progression:
DR = date of disease progression – date of first occurrence of a BOR of PR, CR or SD + 1
- In case of censored information:
DR = date of last tumor assessment – date of first occurrence of a BOR of PR, CR or SD + 1

Note: subjects with only one assessment post baseline with response equal to PD won't be counted for the DR calculation

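### Duration of response includes patients whose best result is stable disease, so the planned outputs would mix non-responders into a result labelled as response

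*SAP*

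**What the plan says.** - **Start of the clock.** SAP 5.4.2 has DoR "defined as time from first occurrence of a BOR of PR, CR or SD as locally assessed, until the disease has been shown to progress". Both formulas in SAP 12.1, for events and for censored cases, subtract the "date of first occurrence of a BOR of PR, CR or SD + 1". The only patients it leaves out are those whose single post-baseline assessment shows PD.
- **Protocol.** The synopsis and section 8.5.5.2 also start DoR at PR, CR or SD. They date it from confirmation, where the SAP says first occurrence.
- **Response elsewhere in SAP 12.1.** "Objective Response Rate (ORR) is calculated as the sum of BOR rates of complete response (CR), partial response (PR"). For disease control: "Disease Control Rate (DCR) is calculated as the sum of BOR rates of complete response (CR), partial response (PR) and stable disease (SD").
- **Deaths.** SAP 5.4.2 says: "Subjects, with a previous response, who do not show a relapse or die without recording a relapse are censored", at the last relapse-free scan. For both DoR and PFS it adds: "Please refer to Attachment A for the complete Censoring Rules list".
- **Outputs.** Figures 6.1 and 6.2 are titled as Kaplan-Meier curves of duration of response (local and central), and Table 3.3 summarises the time-to-event endpoints. Subgroup analyses are marked not applicable (SAP 12.2), and the index in SAP 13.2 lists no CR/PR-only version.

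**The concern.** DoR is normally read next to ORR: it tells the reader how long the counted responses lasted. Here the two rest on different patients. ORR takes CR and PR, while DoR takes the three categories that make up DCR. A patient who never responded therefore contributes a duration, and usually an event, to a curve labelled as response. Because nothing in the planned output isolates CR/PR patients, a reader of the report could not recover how long the responses behind the primary Step 2 endpoint lasted.

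The handling of death is a separate matter. Censoring a patient who dies without recorded relapse treats the death as unrelated to the risk of progression, which is hard to defend in refractory metastatic disease.

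**Working it through.** The documents give no DoR figure and the sample-size text is blacked out, so there is no stated number to reproduce. The check compares definitions and then does simple arithmetic.

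**1. Who enters the set.** ORR numerator = CR + PR. DCR numerator = CR + PR + SD. DoR start = PR, CR or SD. The DoR set equals the DCR numerator.

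**2. Does SD at the first scan qualify?** With 28-day cycles and no visit windows, scans fall on Cycle 3 Day 1 = 2 × 28 + 1 = Day 57, Cycle 5 Day 1 = Day 113 and Cycle 7 Day 1 = Day 169. The scan window opens 7 days earlier, at Day 50. SAP 12.1 requires SD at least six weeks (42 days) after first MEN1611 intake, so SD at the first scheduled scan counts.

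**3. Worked patients**, with the SAP formula (end − start + 1):
- SD at Day 57, PD at Day 113, never a responder: 113 − 57 + 1 = 57 days, with an event.
- PR at Days 57 and 113, death at Day 150 without progression: censored at 113 − 57 + 1 = 57 days. With death as an event: 150 − 57 + 1 = 94 days.

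**4. SD-only share of the set** = SD / (CR + PR + SD), from the response figures in Protocol 6.2:

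| Cited rechallenge study | Inputs | SD-only share | Per 40: responders / SD-only / set |
|---|---|---|---|
| 39-patient retrospective analysis | 19 PR + 2 CR = 21; SD 35.9% = 14/39; DCR 35/39 = 89.7% | 14/35 = 40% | 21.5 / 14.4 / 35.9 |
| CRICKET (phase II) | ORR 23%, DCR 54% | (54 − 23)/54 = 57% | 9.2 / 12.4 / 21.6 |
| E-Rechallenge | PR 15.6% = 5/32; SD 40.6% = 13/32 | 13/18 = 72% | 6.25 / 16.25 / 22.5 |

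Exact 95% intervals are 24–58% for 14/35 and 47–90% for 13/18. The denominator of 32 is back-calculated (the protocol text cites 33 patients). CRICKET gets no exact interval, because 23% is not a whole count of the 28 patients cited (6/28 = 21.4%, 7/28 = 25%); rounding alone gives 56–59%. The figure of 40 is the protocol's number of patients evaluable for efficacy. The share does not depend on how PD or non-evaluable patients are counted; the per-40 counts do.

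**5. Possible effect on a median (assumed inputs).** Let w be the SD-only share and assume exponential durations with a median of 6 months in CR/PR patients and s months in SD-only patients. The pooled median m solves (1 − w)·2^(−m/6) + w·2^(−m/s) = 0.5. For w = 40%, 57% and 72%:
- s = 2: m = 3.7, 3.0 and 2.6 months.
- s = 4: m = 5.1, 4.7 and 4.5 months.

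The component medians are assumptions and appear in neither document.

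**6. Direction of the death rule.** Take three durations: progressions at 113 and 169 days, and a patient last scanned at 57 days who dies at 250. With death as an event the Kaplan-Meier median is 169. Censored at 57, two patients remain at risk, survival falls to 0.5 at 113, and the median is 113 (141 by the midpoint convention). Here censoring shortens the median, whereas the second patient in step 3 shows how it can also remove an event. The sign is not fixed.

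**The case against.** The strongest defence is that the definition is pre-specified, printed openly and the same in category in both documents, and that it feeds a descriptive secondary endpoint with no test. All of that is true and limits the severity. It does not make the label fit the quantity, and no planned output lets a reader separate the two groups. The phrase about a previous response in the censoring sentence hints at responders only, but the formulas name SD. The stated exclusion of patients with a single PD assessment would also be unnecessary if only responders counted.

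The cited studies used other regimens, and this efficacy population also requires two complete cycles, so the shares and counts are indicative only. That part of the defence stands.

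Several stronger readings are tempting, and the documents do not support them:
- *The plan really reports duration of disease control.* It does not. The clock starts at the first qualifying scan, not at first treatment, so that name would also be wrong.
- *Censoring deaths lengthens the estimate.* Step 6 shows that it need not.
- *The censoring table in SAP 12.1 contradicts the DoR text.* Its row "Death without documented progression" has the outcome of progression, and the row "No baseline tumor assessment" censors at first treatment, before a DoR clock could start. But the table directly follows the PFS calculation and precedes a separate DoR formula, so it reads as the PFS table. Only SAP 5.4.2 censors DoR deaths explicitly; the DoR formula does not mention death. Attachment A is not in the available text and cannot be judged.
- *The SAP silently departed from the protocol by replacing confirmation with first occurrence.* The SAP says it reflects protocol version 4.0, and the available protocol is version 5.0. An unlisted departure is not shown.
- *A patient with SD and then PR would start at the SD scan.* BOR is one value per patient, so the first PR is the more natural start.

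**Conclusion.** The point holds. As written, DoR covers CR, PR and SD patients, so its set is the DCR set, and outputs labelled duration of response would include patients who never responded. At the cited rechallenge rates they would be about 40%, 57% and 72% of the set, a majority in two of three studies. This assumes only that the SAP formulas are programmed as printed; the percentages also assume a response mix like that of the cited studies.

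The effect on the reported median is not established. A pooled median lies between those of the two groups, so it would understate DoR if SD-only durations are shorter, as in the assumed example. The censoring of deaths is a weakness of the definition, with no fixed direction of effect. ORR, PFS and OS are untouched. This should be fixed, but it does not threaten the trial's primary result.

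**What to change.** Before database lock:
1. In SAP 5.4.2 and 12.1, define and report DoR in patients with a BOR of CR or PR only, from the first documented CR or PR to progression or death from any cause. State that the missed-assessment rule used for PFS (rows 3 and 4 of the 12.1 table) applies, so that a progression or death after two or more missed scans is censored as it is for PFS.
2. Keep the protocol's SD-inclusive quantity as a separate row under an accurate label, such as *time from first CR, PR or SD assessment to progression*, and not as DoR.
3. Revise the death-censoring sentence in 5.4.2 and the DoR formula in 12.1 to match item 1.
4. Record the change in SAP 3.1 as an added analysis, which Protocol 9.5 allows. If the protocol endpoint is to be replaced and not supplemented, amend the synopsis and section 8.5.5.2 under Protocol 5.7. Use one start term, first documented or confirmed, in both documents.

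The cost is wording in three SAP sections, one further derivation and the matching outputs, with no new data; replacing the endpoint would add a protocol amendment. The downside is a smaller set, about 6 to 22 of 40 patients at the cited rates, with a wider confidence interval and possibly no estimable median.

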5.4.3. Exploratory endpoints

5.4.4. Safety endpoints

The safety endpoints are included among the planned secondary endpoints. Please refer to paragraph 5.4.2.

5.4.5. PK endpoints

The PK profile is a planned secondary endpoint. Please refer to paragraph 5.4.2.

6. General specifications

6.1. Data validation

Medidata Classic Rave ® 2021.1.4 will be used, as Electronic Data Capture system for data entry, by site personnel and for data cleaning and data locking by the Menarini Data Management team.

The eCRF data are elaborated to create the SDTM and ADaM CDISC standard datasets.

6.2. Computer system and software used

The software used for all summary statistics and statistical analyses will be SAS® 9.04.01 and SAS® Studio version 3.8 or higher (SAS Institute, Inc.). All tables and listings will be produced using PROC REPORT or procedure specific output displays using output delivery system (ODS). The summary tables and listings will use SAS monospace font of size 8. The default page type will be A4 and the default page orientation will be landscape.

6.3. Coding systems

6.3.1. Clinical Terms

Concomitant diseases, medical procedures, and Adverse Events will be coded with MedDRA version 23.1 (or newer if available).

